5.0 TREATMENT PLAN

5.1 General

All patients will be registered through CORE. The objective will be to administer AZA or LDAC, and quizartinib at dose level 0 as defined in the Table below. We will first treat 6 patients at dose level -1. If no DLT is identified in >1 patient, this level is defined as MTD and up to 20 patients will be treated at this level with each treatment combination (AC220+ AZA or AC220 + LDAC) for the phase II portion. Other dose levels will be used for dose adjustments for toxicity during therapy.

Approximately 200 patients will be enrolled on this study.

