- 5.2.5** DLT is defined as any clinically significant non-hematologic adverse event or abnormal laboratory value occurring during the first cycle on study unless the event or laboratory value can clearly be determined to be unrelated to AC220 with the following exceptions:
- CTCAE Grade 3 or 4 AST (SGOT) or ALT (SGPT) that resolves to \leq grade 2 in 14 days
 - Grade 3 nausea, vomiting, or diarrhea that can be managed to \leq grade 2 with standard antiemetic or antidiarrheal medications used at prescribed dose within 7 days of onset.
 - Grade 4 vomiting, or diarrhea that can be managed to \leq grade 3 with standard antiemetic or antidiarrheal medications used at prescribed dose within 48 hours of onset.
 - Grade 3 or 4 electrolyte abnormalities will only be considered DLT if possibly related to study drug and not corrected by optimal replacement therapy within 48 hours.
 - Grade 3 biochemical abnormalities of amylase or lipase without evidence of clinical pancreatitis.
 - Grade 3 anorexia or fatigue.
 - Grade 3 or 4 QTc prolongation will constitute DLT as follows: The QTc interval will be calculated by Fridericia's correction factor (QTcF). If the QTc is > 500 msec the EKG must be evaluated within 2 hours in triplicate and if \geq grade 3 QTc prolongation is confirmed this will be considered a DLT.

Hematologic DLT is defined as grade ≥ 3 neutropenia and/or thrombocytopenia with a hypocellular bone marrow lasting for 6 weeks or more after the start of a course in the absence of residual leukemia (i.e., with less than 5% blasts). Anemia will not be considered for the definition of DLT.

- 5.2.5.1** If DLT occurs in $\geq 2/6$ patients, this dose level would exceed the MTD, and an additional 6 patients will be treated at the next lower dose level. The dose level at which 0-1/6 patients experience DLT (but not higher than 60 mg/day) will be used to treat a maximum of 20 patients in each cohort in the phase II portion of the study. If $\geq 2/6$ patients experience DLT at dose level -1 in any arm, dose level -2 may be explored for that arm(s).
- 5.2.5.2** If DLT is observed in 0 or 1/6 in dose level 1, this cohort will be expanded to treat up to 20 patients in the phase II portion of the study. If $\geq 2/6$ patients experience DLT at dose level 1 for any arm of the study, the dose level at which $\leq 1/6$ patients have experienced DLT will be used for the phase II portion of the study for that arm.

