- 5.2.5.3** If DLT is observed in 2/6 patients treated at dose level 1 in any arm, the study will continue at the quizartinib dose of 30 mg PO (dose level -1) for that arm to treat an additional 26 patients at this dose level in the phase II portion of the study.
- 5.2.5.4** Patients that are removed from study before day 28 for any reason other than toxicity and have not experienced DLT will be replaced.
- 5.2.5.5** DLT and MTD will be defined independently for each treatment arm (i.e., AC220 + AZA and AC220 + cytarabine).
- 5.2.6** One cycle of therapy is defined 7 days of AZA or 10 days of LDAC, and 28 days of quizartinib. Patients will receive one cycle of therapy every 4 weeks.
 - 5.2.6.1** Cycles may be started early (but not earlier than day 21) for patients with active disease if judged in the best interest of the patient.
 - 5.2.6.2** Subsequent cycles may be delayed for recovery of toxicity. Delays in start of subsequent cycles greater than 8 weeks should be discussed with the principal investigator.

5.2.6.3 Quizartinib therapy may continue if there is a delay in the start of the next cycle of AZA provided the delay is not due to toxicity possibly related to quizartinib.

5.2.6.4 Subsequent courses may be administered regardless of peripheral blood counts during the first 4 cycles and/or in the presence of residual leukemia. If prolonged myelosuppression (more than 60 days) with evidence of a hypocellular marrow (marrow cellularity less than 5% without evidence of leukemia) is observed subsequent courses of AZA may be given at the next lower dose. If the peripheral counts do not recover (ANC $<1 \times 10^9/L$ and/or platelets $<30 \times 10^9/L$) but there is evidence of residual leukemia in the bone marrow, subsequent cycles can be administered at the discretion of the treating physician not earlier than 3 weeks after the prior cycle.

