12.2 Phase I

The primary objective of the phase I portion of the study is to determine the MTD of each combination therapy. The dose schedule is listed in table 1 of section 5.2.1. Up to 2 dose levels of AC220 will be tested in each combination with a fixed dose of the other drug. Initially, 6 patients will be treated at dose level1, if ≤ 1 patients experience DLT at dose level1, then 6 subsequent patients will be treated at the next higher dose level, dose level2. If ≤ 1 patients experience DLTs in dose level2, this level will be defined as the MTD and will be used in the phase II portion of the study. If > 1 patients experience DLTs at dose level1, then the 6 subsequent patients will be treated at the next lower dose level, level -1. The MTD is defined as the highest dose at which no more than 1 patient experiences DLTs. For each combination therapy, 12 patients will be evaluated. The total sample size for the phase I portion will be 24.

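### Section 5 caps phase II at 20 patients (or 26 more at dose level -1), Section 12.3 plans up to 50 in each of three azacitidine groups, and nothing says which governs

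*Combined protocol and SAP*

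**What the plan says.** Section 5 gives the phase II size four times:

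- Section 5.1: "up to 20 patients will be treated at this level with each treatment combination".
- Section 5.2.5.1: the dose level with 0 or 1 DLT in 6 "will be used to treat a maximum of 20 patients in each cohort in the phase II portion of the study".
- Section 5.2.5.2: with 0 or 1 DLT in 6 at dose level 1, "this cohort will be expanded to treat up to 20 patients in the phase II portion of the study".
- Section 5.2.5.3: "If DLT is observed in 2/6 patients treated at dose level 1 in any arm", the arm continues at dose level -1 "to treat an additional 26 patients at this dose level in the phase II portion of the study".

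Section 5.2.5.1 also says that when a level exceeds the MTD "an additional 6 patients will be treated at the next lower dose level". Section 5.2.3.1 defines a cohort as a dose level, while Sections 4.1.3 and 12.3 use the word for 2A and 2B.

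Section 12.3 plans 26 patients on cytarabine, including 6 from phase I. On azacitidine it plans up to 50 newly diagnosed and up to 50 previously treated Cohort 2A patients, analysed separately, and up to 50 Cohort 2B patients. Monitoring in each azacitidine group starts at 15 patients and continues every 5, with boundaries listed to 45. The credible intervals after Tables 2 and 3 are given for 50 patients.

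On totals, Section 12.2 says "The total sample size for the phase I portion will be 24" and Section 5.1 says "Approximately 200 patients will be enrolled on this study".

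**The concern.** The maximum enrolment for the phase II primary endpoint has two incompatible values for azacitidine. Enrolling the 21st patient in an azacitidine group follows Section 12.3 and breaches the written maximum in Section 5.

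If Section 5 is applied, the monitoring plan in Section 12.3 is not the one that runs. Under 20 or 26 per group the looks at 30 to 45 cannot happen, and under 32 those at 35 to 45 cannot. Tables 2 and 3 and the two credible intervals would then describe a different trial. What is at stake is precision and the validity of the stated operating characteristics. Patient exposure would not rise: early stopping falls largely because accrual ends sooner, and average enrolment falls with it.

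**Working it through.** **What Section 5 can give per group.** The possible sizes are 20 (5.1, 5.2.5.1, 5.2.5.2), 26 (5.2.5.3, or 20 + 6), and at most 26 + 6 = 32 (5.2.5.3 plus the 6 dose-finding patients of 5.2.5.1). None is 50. For cytarabine, Section 5 matches the 26 of Section 12.3 if the 20 excludes the first 6 patients (20 + 6 = 26), or if the 26 in 5.2.5.3 includes the 6 already treated at that level. Read otherwise, cytarabine would be 20 or 32.

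**Totals.**

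| Basis | Sum | Total |
|---|---|---|
| Section 12, phase I counted separately | 24 + 26 + 100 + 50 | 200 |
| Section 12, 6 cytarabine phase I patients counted once | 200 - 6 | 194 |
| Same, with 6 azacitidine phase I patients also counted once | 194 - 6 | 188 |
| Section 5, 20 for each of two combinations | 24 + 40 | 64 |
| Section 5, 20 for each of three combination-by-cohort cells | 24 + 60 | 84 |
| Section 5, 20 for each of four groups | 24 + 80 | 104 |
| Section 5, 26 new patients in each of four groups (upper bound) | 24 + 104 | 128 |

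Only Section 12 is near 200.

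**Reproducing Tables 2 and 3.** Inputs are the printed boundaries for the azacitidine groups at looks 15, 20, 25, 30, 35, 40 and 45:

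- futility in 2A, stop at or below 3, 5, 7, 9, 11, 13, 15 responses;
- futility in 2B, stop at or below 3, 4, 6, 8, 10, 11, 13 responses;
- toxicity, stop at or above 8, 9, 11, 13, 15, 16, 18 patients with DLT.

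These follow from the printed rules: a beta(1,1) prior against 0.5 for 2A, beta(0.6,1.4) against a fixed 0.45 for 2B, and beta(0.6,1.4) against 0.30 for toxicity. With response and toxicity taken as independent, the binomial counts are carried from look to look and paths that cross a boundary are removed. If S_k is the probability of still being open after look k (S_0 = 1) and n_k is the size at that look, then P(stop early) = 1 - S_last and average N = sum of n_k (S_{k-1} - S_k) + N_max × S_last.

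At N_max = 50, stopping probability / average N are:

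| Response/toxicity | Printed | Recomputed |
|---|---|---|
| 2A 0.35/0.1 | 0.584 / 35.8 | 0.584 / 35.76 |
| 2A 0.5/0.1 | 0.055 / 48.6 | 0.055 / 48.59 |
| 2A 0.5/0.5 | 0.96 / 21 | 0.960 / 21.05 |
| 2B 0.3/0.1 | 0.64 / 33 | 0.645 / 33.00 |
| 2B 0.45/0.1 | 0.08 / 47.8 | 0.080 / 47.79 |
| 2B 0.45/0.5 | 0.96 / 20.9 | 0.961 / 20.91 |

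Table 2 stopping probabilities agree within 0.001 in 19 of 20 rows; the exception, 0.65/0.1, is printed as 0.009 and computes as 0.001. Table 3 agrees to about 0.005. With N_max = 46 the stopping columns are unchanged, but the averages drop (2A 0.5/0.1 to 44.82, 2B 0.45/0.1 to 44.11). So the stopping columns need looks out to 45, and the averages need 50.

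**The same recursion with the Section 5 figures applied per group.** For N = 20 the two stopping values are without and with the 20-patient boundary.

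| Response/toxicity | N = 20 | N = 26 | N = 32 | Table (N = 50) |
|---|---|---|---|---|
| 2A 0.35/0.1 | 0.173 or 0.274 / 19.14 | 0.359 / 23.41 | 0.429 / 27.11 | 0.584 / 35.8 |
| 2A 0.5/0.1 | 0.018 or 0.028 / 19.91 | 0.037 / 25.73 | 0.043 / 31.50 | 0.055 / 48.6 |
| 2A 0.5/0.5 | 0.509 or 0.761 / 17.46 | 0.833 / 18.82 | 0.876 / 19.73 | 0.96 / 21 |
| 2B 0.3/0.1 | 0.297 or 0.334 / 18.52 | 0.422 / 22.43 | 0.510 / 25.72 | 0.64 / 33 |
| 2B 0.45/0.5 | 0.521 or 0.766 / 17.39 | 0.836 / 18.73 | 0.879 / 19.63 | 0.96 / 20.9 |

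**Credible intervals.** These are the 2.5% and 97.5% points of beta(a + x, b + N - x), with prior (1, 1) and x = 0.5N for 2A, and prior (0.6, 1.4) and x = 0.45N for 2B (x need not be an integer).

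| N | 2A at 50% | 2B at 45% |
|---|---|---|
| 50, stated | (0.36, 0.64) | (0.31, 0.58) |
| 50, recomputed | (0.366, 0.634) | (0.313, 0.579) |
| 32 | (0.335, 0.665) | (0.281, 0.608) |
| 26 | (0.319, 0.681) | (0.264, 0.623) |
| 20 | (0.298, 0.702) | (0.241, 0.642) |

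**The case against.** The best defence is that Section 12.3 plainly governs. It is specific by group, its looks, boundaries and tables hang together at 50, and the total in Section 5.1 fits nothing else. On that view the caps are residue, the repair is editorial, and no table changes. As a guide to intent this stands. It does not remove the conflict: the total of about 200 sits in the same section as a cap of 20, and the caps are written as maxima in the treatment plan.

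A second objection is that the capped figures above apply 20, 26 or 32 to each group, whereas Section 5.1 counts per combination and Section 5.2.5.3 per arm. That is fair: the per-group figures rest on one reading of the cap, and on a per-arm reading two arms at 26 give 24 + 52 = 76 patients, not 128. But sharing the cap makes the gap larger. With 20 or 26 azacitidine patients spread over three groups, at most one group could reach even the first look at 15, since two would need 30.

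Third, 6 + 20 = 26 explains the cytarabine number and perhaps the 26 in Section 5.2.5.3. This is plausible, and it confines the main conflict to azacitidine, but it cannot produce 50.

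Finally, the stated credible intervals are conditional on reaching 50 patients, so they are correct under that condition. Under a cap the condition is never met and the achieved intervals would be wider.

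**Conclusion.** The inconsistency is real and must be fixed before the phase II size can be treated as defined. Section 12.3 is not miscalculated; it describes a 50-patient design that Section 5 does not permit.

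If a cap applied per group, the half-width of the 2A interval at 50% response would be about 0.20 at N = 20, 0.18 at 26 and 0.165 at 32, against the stated 0.14. In 2B, a true response of 30%, the single-agent rate the combination is meant to improve on, would lead to early stopping with probability 0.30 to 0.51 across those sizes at 10% toxicity, against the printed 0.64.

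These sizes assume independent response and toxicity, the printed boundaries, and one cap per group. That the caps are leftover text is an inference from the total of about 200; the documents do not state it.

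**What to change.** Reconcile Sections 5.1, 5.2.5.1, 5.2.5.2 and 5.2.5.3 with Section 12.3 and state which governs.

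- **If Section 12.3 is intended:** replace the Section 5 caps with its numbers: cytarabine 26 including 6 from phase I; azacitidine Cohort 2A up to 50 newly diagnosed and up to 50 previously treated; Cohort 2B up to 50. This costs protocol wording only, since the total already agrees.
- **In either case:** the sponsor should confirm what the 26 in Section 5.2.5.3 means, whether it includes the 6 dose-finding patients, and which arms it covers. The two uses of the word cohort (dose level in 5.2.3.1, 2A/2B elsewhere) should be separated in the same edit.
- **If a cap is intended for azacitidine:** say whether it applies per combination or per group, then re-run Tables 2 and 3 and restate the looks and boundaries, the credible intervals and the total enrolment for that size.

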5.2.7 Quizartinib Administration

Quizartinib will be administered orally at a starting dose of 60 mg daily for the scheduled 28 days in each cycle.

5.2.7.1 If a dose is missed or vomited, the next dose should not be increased to account for missing a dose. The subject should take the next regular dose at the regularly scheduled time.

5.2.7.2 Treatment may be prolonged beyond the planned 28 days of each cycle if the start of the next cycle of AZA or LDAC is delayed. However, if there are adverse events that mandate treatment interruption or it is considered in the best interest of the patient for safety reasons to interrupt therapy, quizartinib administration can be transiently discontinued and re-started as per guidelines in section 6.0.

5.3 Duration of Therapy

In the absence of treatment delays due to adverse events, treatment may continue until one of the following criteria applies:

1. Clinically significant progressive disease
2. Grade 4 QTc prolongation.
3. Intercurrent illness that prevents further administration of treatment

4. Patient request
5. General or specific changes in the patient's condition render the patient unacceptable for further treatment in the judgment of the investigator.
6. Unacceptable toxicity that in the opinion of the investigator makes it unsafe to continue therapy. This includes patients with grade 4 non-hematological toxicity unless it reverses to grade ≤ 1 on or before 14 days of interrupting AC220.

5.3.1 It is planned that up to a total of 12 cycles of therapy will be administered for patients deriving benefit from this regimen. Continuation of therapy for patients completing 12 cycles of therapy may be considered on a case by case basis after discussion with the principal investigator.

5.3.2 A minimum of 1 full course (defined as the administration of AZA for 7 days or LDAC for 10 days, and quizartinib for 24 days for cycle one, i.e. days 5-28) will be required for a patient to be considered as having received an adequate trial to evaluate efficacy. All patients receiving at least one dose of any of the two drugs will be considered evaluable for toxicity.

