- 2.4 Recently, the results of a randomized trial comparing two lower doses of quizartinib were reported. In this trial, patients with relapsed or refractory AML with FLT3 mutation were randomized to receive quizartinib 30 mg or 60 mg orally, daily. A total of 76 patients were enrolled (38 to each arm). The overall composite response rate (CRc, which was the primary endpoint) was identical for the two arms (47%). The overall response rate was slightly higher with 60 mg daily (71%) than with 30 mg daily (61%) because of a higher rate of partial responses in the 60mg arm (24%) compared to the 30 mg arm (13%). QTc prolongation to >500 msec (the dose limit⁹⁸ toxicity for quizartinib) occurred in only 3% with 60 mg and 5% with 30 mg. When comparing these results with a prior study exploring higher doses (90 mg, 135 mg, and 200 mg) it is clear that the rate of CRc is identical at all dose levels with some increase in PR with progressively higher doses. However, QTc prolongation is clearly dose dependent and prolongations >60 msec from baseline occur in 40% or more of the patients treated at doses of 90mg or above, exceeding the threshold of acceptable grade 3 toxicity for the standard definition of MTD. Although these prolongations have been asymptomatic and transient, resolving with lower doses, based on this new data we have decided not to explore a dose level of 90 mg daily and expand 60

mg (i.e., the starting dose level) for the phase 2 portion of the study provided MTD is not exceeded as defined in the protocol section 5.2.5. If MTD is exceeded at this dose level, 30 mg will be explored.

	2689-CL-2004		AC220-002 (Cohort 2)		
	30 mg/day (N = 38)	60 mg/day (N = 38)	90 mg/day (N=57)	135 mg/day (N=67)	200 mg/day (N=12)
Best Response					
CRc Rate	47%	47%	47%	45%	42%
PR Rate	13%	24%	25%	28%	50%
Maximum change in QTcF from baseline (msec)					
≤ 30	50%	44%	9%	9%	0%
> 30 to ≤ 60	47%	36%	46%	51%	8%
> 60	3%	19%	46%	39%	92%

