4.2 Exclusion Criteria

- 4.2.1 Patients with known allergy or hypersensitivity to quizartinib, mannitol, AZA, cytarabine or any of their components.
- 4.2.2 Patients with electrolyte abnormalities at study entry defined as follows:
 - 4.2.2.1 Serum potassium < 3.5 mEq/L despite supplementation, or > 5.5 mEq/L.
 - 4.2.2.2 Serum magnesium above or below the institutional normal limit despite adequate management.
 - 4.2.2.3 Serum calcium (corrected for albumin levels) above or below institutional normal limit despite adequate management.
- 4.2.3 Patients with known significant impairment of gastrointestinal (GI) function or GI disease that may significantly alter the absorption of quizartinib.
- 4.2.4 Patients with any other known disease concurrent severe and/or uncontrolled medical condition (e.g. uncontrolled diabetes, cardiovascular disease including congestive heart failure, myocardial infarction within 6 months and poorly controlled hypertension, chronic renal disease, or active uncontrolled infection) which could compromise participation in the study. Patients with current active malignancies or any remission for < 6 months, except patients with carcinoma in situ or with non-melanoma skin cancer who may have active disease or be in remission for less than 6 months.
- 4.2.5 Patients with a known confirmed diagnosis of HIV infection or active viral hepatitis.
- 4.2.6 Patients who have had any major surgical procedure within 14 days of Day 1.
- 4.2.7 Patients with known malignant disease of the central nervous system.
- 4.2.8 Impaired cardiac function including any of the following
 - 4.2.8.1 Screening ECG with a QTc > 450 msec. The QTc interval will be calculated by Fridericia's correction factor (QTcF) at Screening and on Day 5 prior to the first dose of AC220. The QTcF will be derived from the average QTcF in triplicate. If QTcF > 450 msec on Day 5, AC220 will not be given.
 - 4.2.8.2 Patients with congenital long QT syndrome

- 4.2.8.3 History or presence of sustained ventricular tachycardia requiring medical intervention
 - 4.2.8.4 Any history of clinically significant ventricular fibrillation or torsades de pointes
 - 4.2.8.5 Known history of second or third degree heart block (may be eligible if the patient currently has a pacemaker)
 - 4.2.8.6 Sustained heart rate of <50/minute on pre-entry ECG
 - 4.2.8.7 Right bundle branch block + left anterior hemiblock (bifascicular block)

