Cardiac Toxicity	QTc > 480 and ≤ 500 msec	Check magnesium and potassium levels and correct any abnormalities. If possible, stop any medications that may prolong the QTc interval. Decrease AC220 to next lowest dose level until QTc interval improves to ≤480 msec. AC220 dose may then be escalated to the previous dose if other external factors have been corrected and QTc has remained below 480 msec in at least 3 consecutive ECG separated for at least 2 weeks.
Cardiac Toxicity	QTc interval >500 msec	Check magnesium and potassium levels and correct any abnormalities. Interrupt AC220 and if possible any medications that may prolong the QTc interval. If QTc interval resolves to within 30 msec of baseline value within 7 days resume AC220 at the next lower dose level. If not resolved within 7 days, discontinue therapy permanently.
Cardiac Toxicity	QTc interval >500 or >60 ms change from baseline, and Torsade de pointes or polymorphic ventricular tachycardia or signs/symptoms of serious arrhythmia (i.e., grade 4)	Discontinue therapy

6.3.1 Patients in whom the toxicity occurs or persists beyond the planned completion of drug administration for the cycle will have the dose reductions implemented in subsequent cycles provided the toxicity has resolved as specified in the table above.

6.3.2 If adverse events are clearly associated with one of the drugs, dose adjustments to only that agent may be performed.

- 6.3.3** Dose modifications different than those described above (e.g., dose reductions by 2 dose levels, decreased number of days of administration of either drug continuation of only quizartinib) may be implemented if judged in the best interest of the patient after discussion with the PI and documentation of the rationale for this action.
- 6.3.4** Dose adjustments for only of the drugs may be considered when the adverse event may be clearly associated with only one drug (e.g., QTc prolongation with quizartinib).
- 6.3.5** Patients in whom therapy is held for > 8 weeks due to toxicity will be removed from the trial.

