12.3 Phase II

A: Cohort 2A – FLT3-ITD

The primary endpoint of the phase II portion of the study is overall response (CR+Cri+PR+HI) (first 2 treatment courses). It would be encouraging if the overall response rate reaches 50%.

Treatment with AC220 + low-dose cytarabine (Cohort 2A-FLT3-ITD)

Patients enrolled in the treatment of AC220 + low-dose cytarabine could be newly diagnosed or previously treated. A total of 26 patients (including 6 patients treated at MTD in Phase I) will be treated with this treatment combination. The toxicity and efficacy (CR+Cri+PR+HI) will be monitored during the study, and all the data will be used to update the prior distributions for toxicity and efficacy parameters. The study will be stopped for toxicity and futility based on the following stopping rules. If the trial for this treatment continues until 26 patients are evaluated, and assuming the overall response rate is 50%, then the 95% credible interval for overall response rate would be (0.32, 0.68).

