12.3.2 Toxicity

Toxicity will be monitored closely using the method of Thall et al (1995). Denote the probability of toxicity by θ_E , where toxicity is defined as DLTs. We assume $\theta_E \sim \text{beta}(0.6, 1.4)$. We will stop the trial if at any point $\Pr(\theta_E > 0.30 \mid \text{data}) > 0.9$. That is, we will stop the trial of this combination therapy if, at any time during the study, we determine that there is more than 90% chance that the toxicity rate is more than 30%. The trial will be stopped if (the number of toxicity observed / among number of patients) $\geq 6/11, 7/14, 8/16, 9/19, 10/22$ and $11/24$.

Table 1 presents operating characteristics for the study design.

Table 1: Operating characteristics

Response rate	Toxicity rate	Probability of early stopping	Average number of patients
0.2	0.1	0.862	15.01
	0.2	0.864	14.94
	0.3	0.884	14.48
	0.4	0.929	13.37
	0.5	0.974	11.95
0.3	0.1	0.497	20.31
	0.2	0.508	20.14
	0.3	0.579	19.11
	0.4	0.743	16.64
	0.5	0.907	13.62
0.4	0.1	0.175	24.02
	0.2	0.192	23.79
	0.3	0.309	23.33
	0.4	0.577	18.88
	0.5	0.847	14.72
0.5	0.1	0.038	25.54
	0.2	0.058	25.29
	0.3	0.194	23.65
	0.4	0.507	19.79
	0.5	0.822	15.16
0.6	0.1	0.005	25.93
	0.2	0.026	25.67
	0.3	0.167	23.99
	0.4	0.49	20.02
	0.5	0.816	15.27

MultcLean V1.2 developed in the Department of Biostatistics MDACC was used to calculate the stopping boundaries for futility and toxicity monitoring rules.

Treatment with AC220 + 5-azacytidine (Cohort 2A-FLT3-ITD)

Up to 50 newly diagnosed patients (including patients treated at the same dose in phase I) and up to 50 previously treated patients (including patients treated at the same dose in phase I) will be treated with AC220 + 5-azacytidine. The analysis for the two groups of patients will be completed separately.

The study will monitor futility and safety for each patient group and the monitoring will begin when 15 patients have been enrolled in that group, and thereafter by a cohort of 5 patients. The trial in one group will be stopped early if at any time point the data in that group suggest

$$\Pr(P_E < 0.5 \mid \text{data}) > 0.98 \text{ or}$$

$$\Pr(\theta_E > 0.30 \mid \text{data}) > 0.9$$

Where P_E denote the response rate for experimental treatment, and θ_E denotes the toxicity rate for the experimental treatment combination. Assume $P_E \sim$ prior beta(1,1) and $\theta_E \sim$ prior beta(0.6, 1.4).

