Where P_E and P_S denote the response rate for experimental and standard treatment, respectively, and θ_E denotes the toxicity rate for the experimental treatment combination. Assume $P_E \sim$ prior beta(0.6, 1.4) and $\theta_E \sim$ prior beta(0.6, 1.4).

That is, the trial in this cohort will be stopped early for futility if the data indicate that there is more than 98% probability that the response rate is not improved by 15% or the trial will be stopped early for toxicity if the data indicate that there is more than 90% probability that the toxicity rate (i.e. DLT rate) is more than 30%. The corresponding stopping boundaries for futility is: the trial in this cohort will be stopped early if (the number of response observed / among number of patients) in this cohort $\leq 3/15, 4/20, 6/25, 8/30, 10/35, 11/40$ and $13/45$.

The corresponding stopping boundaries for toxicity is: The trial will be stopped early in this cohort if (the number of patients experienced DLTs / among number of patients) in this cohort $\geq 8/15, 9/20, 11/25, 13/30, 15/35, 16/40$ and $18/45$.

Table 3 presents the operating characteristics for the above design.

Table 3: OCs for the design for cohort 2B

Response rate	Toxicity rate	Probability of early stopping	Average number of patients
0.3	0.1	0.64	33
0.3	0.3	0.72	30.6
0.3	0.5	0.99	18.8
0.45	0.1	0.08	47.8
0.45	0.3	0.27	43
0.45	0.5	0.96	20.9
0.6	0.1	0.002	49.9
0.6	0.3	0.21	44.8
0.6	0.5	0.96	21.2

If the trial in one group continues until 50 patients are evaluated, and assuming the overall response rate is 45%, then the 95% credible interval for overall response rate would be (0.31, 0.58).

12.4 Analysis Plan:

For discrete or categorical data, descriptive statistics will include tabulations of frequencies. For continuous data, summary statistics including n, mean, standard deviation, median, minimum and maximum will be computed. The posterior response rate and its 95% credible intervals will be estimated.

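### Section 5.3.2 ties efficacy evaluability to completing course 1, and 12.3–12.4 name no analysis set, so the primary response rate can be computed in completers only and read too high

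*Combined protocol and SAP*

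**What the plan says.** Section 5.3.2 (Duration of Therapy) holds the only rule in the documents on who can be assessed for efficacy. A full first course, meaning azacitidine for 7 days or cytarabine for 10 days together with quizartinib on days 5–28, "will be required for a patient to be considered as having received an adequate trial to evaluate efficacy". The next sentence makes anyone who received a single dose of either drug evaluable for toxicity.

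Section 12.3 sets the phase II primary endpoint as overall response in the first 2 courses. For cohort 2A it adds: "It would be encouraging if the overall response rate reaches 50" percent. For cohort 2B the goal is 45%. Section 12.4 says of the final analysis only that "The posterior response rate and its 95% credible intervals will be estimated".

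The denominator is described in several ways:
- For the cytarabine arm, "all the data will be used to update the prior distributions for toxicity and efficacy parameters".
- For the azacitidine groups, "the monitoring will begin when 15 patients have been enrolled in that group"; cohort 2B uses similar wording.
- The stopping boundaries count responses against the number of patients.
- The planned credible intervals are stated for 26 or 50 patients *evaluated*, a word that is not defined.

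Neither 12.3 nor 12.4 refers to 5.3.2.

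**The concern.** The 5.3.2 condition is settled after treatment starts and is related to outcome. Patients who die, progress or stop during course 1 fail it, and most of them will be non-responders. If it defines the denominator of the final estimate, those non-responders disappear from the rate.

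The contrast with the one-dose toxicity rule makes the narrower efficacy set the natural reading, although 5.3.2 does not say that anyone is excluded. Because section 12 is silent, an analyst could report either set and still be following the protocol, and could make that choice after seeing the data.

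The response rate is the phase II primary result, the arms have no randomised control, and the rate will be read against 50% (2A) or 45% (2B). There is no final hypothesis test, so what is at stake is an overstated estimate and interval rather than a type I error. The interim wording points to all patients. The exposure is therefore mainly in the final estimate, which could rest on a different set from the one monitored.

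**Working it through.** **1. The plan's own figures reproduce.** With a beta(1,1) prior and 13/26 responses, the posterior is beta(14,14), with 95% limits 0.3195 and 0.6805; section 12.3 states (0.32, 0.68). An exact recursion over the azacitidine futility looks (stop at ≤3/15, 5/20, 7/25, 9/30, 11/35, 13/40, 15/45), ignoring toxicity stopping, gives at a true 35% a stopping probability of 0.584 and a mean of 35.8 patients. Table 2 gives 0.584 and 35.8 at toxicity 0.1. For cohort 2B at a true 30% the same method gives 0.645 and 33.0; Table 3 gives 0.64 and 33. The design arithmetic is not in question.

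**2. Who fails the 5.3.2 condition.**
- Patients who die, progress or stop in course 1 (5.3).
- Patients with QTc above 500 msec in course 1, for whom 6.3 says: "Interrupt AC220 and if possible any medications that may prolong the QTc interval".
- Patients who never start quizartinib under 4.2.8.1: "If QTcF > 450 msec on Day 5, AC220 will not be given".

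**3. Share excluded, x.** The documents give none, so x = 3–20% is an assumption. For the low end, section 2.4 reports that QTc above 500 msec on monotherapy "occurred in only 3% with 60 mg and 5% with 30 mg", not stated to be a first-cycle rate. For the high end the only marker is loose: section 2.3 reports 22% mortality within 7 weeks in patients aged 65 or older, over a longer window and on other therapy.

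**4. Rate in the 5.3.2 set.** Let p be the all-treated rate and q the response rate among those excluded. Then

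rate = (p − x·q) / (1 − x).

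For example, with p = 0.40, x = 0.10 and q = 0: 0.40/0.90 = 0.444. With q = 0.20 (assumed): (0.40 − 0.02)/0.90 = 0.422.

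| p = 0.40 | x = 3% | 5% | 10% | 20% |
|---|---|---|---|---|
| q = 0 (upper bound) | 41.2% | 42.1% | 44.4% | 50.0% |
| q = 0.20 | 40.6% | 41.1% | 42.2% | 45.0% |

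With 20 responders among 50 treated and a beta(1,1) prior, the reported result is:
- 20/50 = 40% (0.28–0.54) in all treated;
- 20/45 = 44% (0.31–0.59) with 5 non-responders dropped;
- 20/40 = 50% (0.35–0.65) with 10 dropped.

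**5. Chance of reaching 50 patients and reporting at least the reference rate.** This is an exact joint recursion over completers, their responses, and responses among those excluded. Futility looks use all enrolled patients, as the text indicates, and toxicity stopping is ignored.

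| Group, true rate, reference | All treated | q | x = 3% | 5% | 10% | 20% |
|---|---|---|---|---|---|---|
| Azacitidine 2A, 40%, ≥50% | 0.097 | 0 | 0.122 | 0.151 | 0.243 | 0.480 |
| | | 0.20 | 0.105 | 0.119 | 0.161 | 0.277 |
| Azacitidine 2A, 35%, ≥50% | 0.021 | 0 | 0.028 | 0.037 | 0.073 | 0.207 |
| | | 0.20 | 0.023 | 0.026 | 0.039 | 0.082 |
| Cohort 2B, 30%, ≥45% | 0.012 | 0 | 0.017 | 0.024 | 0.049 | 0.147 |
| | | 0.20 | 0.013 | 0.016 | 0.025 | 0.049 |

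Because the looks count everyone, the futility stopping probability does not depend on x (0.336 at a true 40%, 0.584 at 35%).

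**The case against.** The strongest reply is that the text already leans towards all patients. The cytarabine section updates its priors with all the data, that update yields the posterior that 12.4 reports, and 12.4 introduces no second population. Section 10 defines responders as those who obtain a response, so someone who dies early is not one. On this reading 5.3.2, placed under Duration of Therapy, only states the exposure needed before judging the drug in a given patient. This is a fair reading, but nothing in section 12 makes it binding, and 5.3.2 remains the only written efficacy-evaluability rule.

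A second reply concerns *evaluated*. If it means 5.3.2-evaluable, the final intervals would rest on 26 or 50 completers, not on 45 or 40. That would change the example counts and the step 5 probabilities. The formula in step 4 does not involve N, so the bias in the rate would remain.

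A third is that size and direction are assumed. This stands in part. A patient whose quizartinib is held for QTc also fails the rule and may later respond. If excluded patients respond at the same 40% as everyone else, the 0.097 becomes 0.090–0.113 across x = 3–20%, which is essentially no bias. If they respond at 60%, it falls to 0.031–0.077. The 0.480 figure needs both 20% exclusion and no response among those excluded. At 3–5%, the only shares tied to quizartinib data, the effect is small.

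Finally, reporting at least 50% is not a decision rule in the protocol. That is correct, and the probabilities in step 5 only describe how the result would read.

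**Conclusion.** The concern holds and should be fixed. The plan contains a completion-based efficacy rule and nothing that keeps it out of the primary estimate. If it is applied, the rate is biased upward whenever excluded patients respond less often than completers, which is likely for early death or progression but not certain for QTc holds.

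The effect is minor at 3–5% exclusion and material from about 10%, where a true 40% reads as 42.2–44.4%. These sizes rest on the assumed exclusion share and on an assumed response rate of 0 to 20% among those excluded. Toxicity monitoring is not affected. The futility operating characteristics in Tables 1–3 would change only if 5.3.2 were also applied at the looks, which the text does not favour. Confidence is medium, because 5.3.2 permits the completer reading without requiring it.

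**What to change.** - **Primary set (12.3–12.4).** State that the primary response analysis and the futility counts include every patient given at least one dose of study treatment at the phase II dose, including phase I patients carried forward.
- **Missing outcomes (12.3–12.4).** State that anyone without a documented response in the first 2 courses counts as a non-responder, including after early death, withdrawal or a missing marrow.
- **Sensitivity analysis (5.3.2, 12.4).** Keep the 5.3.2 set as a named sensitivity analysis, with a cross-reference from 12.4.
- **Replacement (5.2.5.4).** Note that replacing a patient for DLT assessment does not remove that patient from the response denominator.

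The cost is a few sentences in 5.3.2, 12.3 and 12.4 and one note at 5.2.5.4, with no extra patients or procedures and no change to treatment rules. The reported rate will be somewhat lower than in a completer analysis. If an all-treated analysis is already intended, the change only puts that in writing.
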